9.6.2 Analysis of Secondary Efficacy Endpoints

The analysis of all secondary endpoints will be based on the Efficacy Evaluable Set. Sensitivity of the primary analysis will be performed using the PPS.

9.6.2.1 HI-E Criteria > 8 weeks

The HI-E criteria of ≥ 8 weeks will also be evaluated following 16 and 48 weeks of treatment. The summary and analysis at Weeks 16 and 48 will follow the same methodology as the primary endpoint.

9.6.2.2 HI-E criteria \geq 16 weeks

The incidence of HI-E responses lasting 16 weeks or longer within 24 and 48 weeks of etavopivat treatment, will be evaluated using the following 3 conditions:

- NTD: ≥ 1.5 g/dL increase from baseline maintained for at least 16 consecutive weeks
- LTB: no transfusion for at least 16 weeks
- HTB: reduction by $\geq 50\%$ in RBC units for at least 16 consecutive weeks.

Responses will be summarized and analyzed with the same methodology as the primary endpoint.

9.6.2.3 Additional Measures of Clinical Benefit

Additional measures of potential clinical benefit will be summarized with descriptive statistics. These consist of the following:

- Overall Response Rate (2006 IWG Criteria)
- Duration of response (2006 IWG Criteria)
- Increase in neutrophils and/or platelets
- Decrease in ferritin and decrease in iron chelation therapy
- Overall survival
- Reduction in RBC transfusions and rate of RBC transfusion independence (RBC-TI) in patients with LTB or HTB at study entry

The Overall Response Rate (ORR) and duration of response are based on the 2006 IWG Criteria (Cheson et al. 2006) as assessed at each scheduled assessment. ORR will be summarized with descriptive statistics by disease strata and overall. Duration of response will be summarized with quantiles based on product limit estimates (ie, Kaplan-Meier). Duration of response is defined as the time from date of first known incidence of a 2006 IWG criteria response to the most recent date that the 2006 IWG criteria is not met following the initial response. If the subject has met IWG criteria throughout the period following the initial response, the subject will be censored at the latest date of end of study, loss to follow-up, or death.

Overall survival is defined as the time from first dose to date of death. If the subject was alive at last contact, the end date will be censored at the latest of either end of study, loss to follow-up, or study discontinuation. Overall survival will be summarized with quantiles based on product limit estimates, in the same manner as the duration of response.

Laboratory results and change from baseline will be summarized with descriptive statistics for neutrophils and platelets. On-study use of iron chelation therapies will also be summarized with descriptive statistics. The study SAP will detail chelation therapy strata and summary methods as required.

For LTB and HTB patients, RBC transfusions will be summarized by both unit and volume with descriptive statistics by nominal visit. The incidence of 56-day transfusion independence by Week 16, Week 24, and Week 48 and duration of transfusion independence will be summarized with descriptive statistics.

9.6.3 PK/PD and Exploratory Efficacy Analyses

Etavopivat plasma concentrations will be summarized descriptively by time point, disease strata (NTD, LTB, and HTB), and overall.

Pharmacokinetic parameters will be based on the actual sample collection times and determined using standard noncompartmental methods. Pharmacokinetic analyses will be conducted on patients in the Pharmacokinetic Set and will be detailed in a separate PK plan.

Pharmacodynamic (PD) results will include RBC 2,3-DPG and ATP levels over time. All PD endpoints will be based on the efficacy evaluable set and will be summarized with descriptive statistics by time point, disease strata, and overall.

9.6.3.1 Pharmacokinetic and/or Pharmacodynamic Modelling

Data from the study may be used for exploratory pharmacokinetic and/or pharmacodynamic analysis as needed.

9.7 Analysis of Study Population Endpoints

All study population analyses will be conducted on the Full Analysis Set.

9.7.1 Disposition and Reasons for Discontinuation

The number of patients completing informed consent, dosed, completing the study, early discontinuation, and treatment discontinuation will be summarized with descriptive statistics for each disease strata (NTD, LTB, and HTB) and overall. The number of patients in each analysis population will also be summarized.

All protocol deviations related to study inclusion or exclusion criteria, conduct of the trial, patient management, or patient assessment will be listed, as well as the major/minor status and the effect on the per-protocol set (PP).

9.7.2 Demographics and Other Baseline Characteristics

Demographics and baseline characteristics will be summarized for each disease strata and overall using descriptive statistics.

9.7.3 Study Drug Compliance

Study drug compliance will be assessed by examination of the dispensed and returned pills. Percent compliance will be calculated based on comparing the returned pills to the expected number of pills to be taken between visits.

Study drug compliance will be summarized using descriptive statistics for each disease strata and overall.

9.8 Analysis of Safety Assessments

All Safety analyses will be performed on the Safety Set.

9.8.1 Adverse Events

Original verbatim terms used in the eCRFs by Investigators or designees to identify AEs will be coded using Medical Dictionary for Regulatory Activities (MedDRA), version 21.0 or higher.

Summaries of AEs will be based on TEAEs. A TEAE is an AE that begins or worsens following first dose of study drug and prior to 28 days after the last dose of study drug. The number and percentage of patients with TEAEs will be summarized for each disease strata, and overall, by MedDRA System Organ Class (SOC) and Preferred Term (PT) for the following categories:

- TEAEs
- Drug-Related TEAEs
- Grade 3 or Higher TEAEs
- Grade 3 or Higher Drug-Related TEAEs
- Serious TEAEs
- Serious Drug-related TEAEs
- TEAEs Leading to Dose Reduction
- TEAEs Leading to Dose Interruption
- TEAEs Leading to Dose Discontinuation

Maximum Severity of TEAEs will also be summarized by SOC and PT. Additional summary tabulations of TEAEs may also include: most commonly reported TEAEs, deaths, serious TEAEs, serious drug-related TEAEs, TEAEs leading to dose reduction, TEAEs leading to dose interruption, and TEAEs leading to study drug discontinuation will be also provided, summarized by SOC and PT.

All adverse events will be presented in data listings with non-treatment-emergent events being included in a separate listing.

9.8.2 Other Safety Assessments

Vital signs may include blood pressure (systolic and diastolic), heart rate, respiratory rate, and oral temperature. Descriptive statistics of each collected vital sign will be summarized for each disease

strata and overall. Temporal assessments will include both raw and change from baseline summaries for each time point.

ECG result interpretations will be summarized with descriptive statistics for each disease strata and overall. Quantitative ECG results will be summarized in the same manner as vital signs for the PR, QT, QRS, HR, and QT interval corrected using Fridericia's correction formula (QTcF). Additionally, categories of quantitative results and shift tables may be included with details included in the SAP.

Laboratory test data will be summarized descriptively by the type of laboratory test and nominal visit (absolute value and change from baseline) and disease strata and overall. Shift tables may be produced for selected laboratory test results based on clinical interpretations and NCI-CTCAE severity level thresholds. Details of these analyses will be included in the SAP.

Concomitant medications and prior systemic therapies will be coded using the World Health Organization Drug Dictionary (WHODrug) into Anatomical Therapeutic Chemical (ATC) and PT. The number and percentage of subjects taking concomitant medications will be tabulated by ATC, PT, disease strata, and overall.

Physical examination results will be included in data listings.

10.0 DATA MANAGEMENT AND RECORD KEEPING

10.1.1 Data Handling

Data will be recorded on eCRFs and reviewed by the clinical research associate (CRA), data manager and/or Sponsor representative. The CRAs will verify data recorded in the relevant system(s) with source documents. All corrections or changes made to any study data must be appropriately tracked in an audit trail in the relevant system. An eCRF will be considered complete when all missing, incorrect, and/or inconsistent data has been accounted for.

10.1.2 Computer Systems

Data will be processed using a validated computer system conforming to regulatory requirements.

10.1.3 Data Entry

Data must be recorded using the relevant system while the study is in progress. All site personnel must log into the system using their secure username and password in order to enter, review, or correct study data. These procedures must comply with Title 21 of the Code of Federal Regulations (21 CFR Part 11) and other appropriate international regulations. All passwords will be strictly confidential.

10.1.4 Medical Information Coding

For medical information, the following thesauri will be used:

- MedDRA for medical history and adverse events
- WHODrug for prior and concomitant medications and prior systemic therapies

10.1.5 Data Validation

Validation checks programmed within the relevant system, as well as supplemental validation performed via review of the data, will be applied to the data in order to ensure accurate, consistent, and reliable data. Data identified as erroneous, or data that are missing, will be referred to the investigative site for resolution through data queries.

The eCRFs must be reviewed and electronically signed by the Investigator.

10.2 Record Keeping

Records of patients, source documents, monitoring visit logs, eCRFs, inventory of study product, regulatory documents, and other Sponsor correspondence pertaining to the study must be kept in the appropriate study files at the site. Source data are defined as all information in original records and certified copies of original records of clinical findings, observations, or other activities in a clinical study necessary for the evaluation and reconstruction of the clinical study. Source data are contained in source documents (original records or certified copies). These records will be retained in a secure file for the period as set forth in the Clinical Study Agreement. Prior to transfer or destruction of these records, the Sponsor must be notified in writing and be given the opportunity to further store such records.

11.0 INVESTIGATOR REQUIREMENTS AND QUALITY CONTROL

11.1 Ethical Conduct of the Study

Good Clinical Practice (GCP) is an international ethical and scientific quality standard for designing, conducting, recording, and reporting studies that involve human subjects. Compliance with this standard provides public assurance that the rights, safety, and wellbeing of study subjects are protected, consistent with the principles that have their origin in the Declaration of Helsinki, and that the clinical study data are credible.

11.2 Institutional Review Board/ Independent Ethics Committee

The IRB/ IEC will review all appropriate study documentation in order to safeguard the rights, safety, and well-being of patients. The study will only be conducted at sites where IRB/ IEC approval has been obtained. The protocol, Investigator's Brochure, ICF, advertisements (if applicable), written information given to the patients, safety updates, annual progress reports, and any revisions to these documents will be provided to the IRB/ IEC by the Investigator.

Federal regulations and International Council for Harmonisation (ICH) Guidelines require that approval be obtained from an IRB/ IEC prior to participation of patients in research studies. Prior to study onset, the protocol, any protocol amendments, ICFs, advertisements to be used for patient recruitment, and any other written information regarding this study to be provided to a patient or patient's legal guardian must be approved by the IRB/ IEC.

No drug will be released to the site for dosing until written IRB/ IEC authorization has been received by the Sponsor.

11.3 Informed Consent

The ICF and any changes to the ICF made during the course of the study must be agreed to by the Sponsor or designee and the IRB/ IEC prior to its use and must be in compliance with all ICH GCP, local regulatory requirements, and legal requirements.

The Investigator must ensure that each study patient is fully informed about the nature and objectives of the study and possible risks associated with participation and must ensure that the patient has been informed of his/her rights to privacy. The Investigator will obtain written informed consent from each patient before any study--specific activity is performed and should document in the source documentation that consent was obtained prior to enrollment in the study. The original signed copy of the ICF must be maintained by the Investigator and is subject to inspection by a representative of the Sponsor, their representatives, auditors, the IRB/ IEC and/ or regulatory agencies. A copy of the signed ICF will be given to the patient.

11.4 Study Monitoring Requirements

It is the responsibility of the Investigator to ensure that the study is conducted in accordance with the protocol, Declaration of Helsinki, ICH GCP, and applicable regulatory requirements, and that valid data are entered into the eCRFs.

To achieve this objective, the monitor's duties are to aid the Investigator and, at the same time, the Sponsor in the maintenance of complete, legible, well organized and easily retrievable data. Before the enrollment of any patient in this study, the Sponsor or their designee will review with the

Investigator and site personnel the following documents: protocol, Investigator's Brochure, eCRFs and procedures for their completion, informed consent process, and the procedure for reporting SAEs.

The Investigator will permit the Sponsor or their designee to monitor the study as frequently as deemed necessary to determine that data recording and protocol adherence are satisfactory. During the monitoring visits, information recorded on the eCRFs will be verified against source documents and requests for clarification or correction may be made. After the eCRF data are entered by the site, the CRA will review the data for safety information, completeness, accuracy, and logical consistency. Computer programs that identify data inconsistencies may be used to help monitor the clinical study. If necessary, requests for clarification or correction will be sent to Investigators. The Investigator and his/ her staff will be expected to cooperate with the monitor and provide any missing information, whenever possible.

All monitoring activities will be reported and archived. In addition, monitoring visits will be documented at the investigational site by signature and date on the study-specific monitoring log.

11.5 Visits and Assessments in Emergency Situations

In the event of local or widespread emergencies (eg, COVID-19, weather-related emergencies), inperson clinic visits may present excessive risks or difficulties for study participants and site staff. In these situations, in-person visits may be replaced by alternate methods to assess patients. Arrangements should be made to ensure all samples are collected for laboratory analyses and that study patients have an adequate supply of study drug. Such changes to the research plan should be first discussed with the Medical Lead and must be documented in the study files.

11.6 Disclosure of Data

Data generated by this study must be available for inspection by the FDA, the Sponsor or their designee, applicable foreign health authorities, and the IRB as appropriate. Patients or their legal representatives may request their medical information be given to their personal physician or other appropriate medical personnel responsible for their welfare.

Patient medical information obtained during the study is confidential and disclosure to third parties other than those noted above is prohibited.

11.7 Retention of Records

To enable evaluations and/or audits from regulatory authorities or the Sponsor, the Investigator will keep records, including the identity of all participating patients (sufficient information to link records, eg, eCRFs and hospital records), all original signed ICFs, copies of all eCRFs, SAE forms, source documents, and detailed records of treatment disposition. The records should be retained by the Investigator according to specifications in the ICH guidelines, local regulations, or as specified in the Clinical Study Agreement, whichever is longer. The Investigator must obtain written permission from the Sponsor before disposing of any records, even if retention requirements have been met.

If the Investigator relocates, retires, or for any reason withdraws from the study, the Sponsor should be prospectively notified. The study records must be transferred to an acceptable designee, such as another Investigator, another institution, or to the Sponsor.

11.8 Publication Policy

Following completion of the study, the data may be considered for publication in a scientific journal or for reporting at a scientific meeting. Each Investigator is obligated to keep data pertaining to the study confidential. The Investigator must consult with the Sponsor before any study data are submitted for publication. The Sponsor reserves the right to deny publication rights until mutual agreement on the content, format, interpretation of data in the manuscript, and journal selected for publication are achieved.

13.0 APPENDICES

APPENDIX A: RESPONSE CRITERIA FOR MDS

Adapted from IWG Response Criteria for MDS (Cheson et al. 2006)

Response Category	Response criteria (responses must last at least 4 wks)			
Complete remission (CR)	• Bone marrow: ≤ 5% myeloblasts with normal maturation of all cell lines*			
	Persistent dysplasia will be noted*			
	Peripheral blood‡:			
	o Hb ≥ 11 g/dL			
	○ Platelets $\geq 100 \times 10^9/L$			
	○ Neutrophils $\ge 1.0 \times 10^9 / L$			
	o Blasts 0%			
Partial remission (PR)	All CR criteria if abnormal before treatment except:			
	 Bone marrow blasts decreased by ≥ 50% over pretreatment but still > 5% 			
	Cellularity and morphology not relevant			
Marrow CR	Bone marrow: $\leq 5\%$ myeloblasts and decrease by $\geq 50\%$ over pretreatment			
	Peripheral blood: if HI responses, they will be noted in addition to marrow CR			
Stable disease (SD)	Failure to achieve at least PR, but no evidence of progression for > 8 wks			
Relapse after CR or PR	At least 1 of the following:			
	Return to pretreatment bone marrow blast percentage			
	• Decrement of ≥ 50% from maximum remission/response levels in			
	granulocytes or platelets			
	• Reduction in Hb concentration by ≥ 1.5 g/dL or transfusion dependence			
Disease progression (PD)	For patients with:			
	• Less than 5% blasts: ≥ 50% increase in blasts to > 5% blasts			
	• 5%-10% blasts: ≥ 50% increase to > 10% blasts			
	• 10%-20% blasts: ≥ 50% increase to > 20% blasts			
	• 20%-30% blasts: \geq 50% increase to \geq 30% blasts			
	Any of the following:			
	• At least 50% decrement from maximum remission/response in granulocytes or			
	platelets			
	• Reduction in Hb by ≥ 2 g/dL			
	Transfusion dependence			

Hb = hemoglobin; HI = hematologic improvement; IWG = International Working Group; MDS = myelodysplastic syndromes; wks = weeks.

^{*}Dysplastic changes should consider the normal range of dysplastic changes.

[‡] Transient cytopenias during repeated chemotherapy courses should not be considered as interrupting durability of response, as long as they recover to the improved counts of the previous course.

RESPONSE CRITERIA FOR MDS (continued)

Modified International Working Group Response Criteria for Hematologic Improvement (Updated 2018)

Hematologic Improvement		Response Criteria			
Erythroid	Non-transfused	At least 2 consecutive Hb measurements ≥1.5 g/dL for a period of minimum			
Response	(NTD)*	8 wk in an observation period of 16 to 24 wk compared with the lowest mean			
(HI-E)		of 2 Hb measurements (apart from any transfusion) within 16 wk before			
		treatment onset			
	Low transfusion	Absence of any transfusions for at least 8 wk in an observation period of			
	burden (LTB)	16-24 wk with the same transfusion policy (defined below) compared with			
		16 wk prior to treatment			
	High	Major response: Transfusion independence, defined by the absence of any			
	transfusion	transfusions over a period of minimum 8 wk in an observation period of			
	burden (HTB)	16-24 wk with the same transfusion policy (defined below) compared with			
		16 wk prior to treatment			
		Minor response: Reduction by at least 50% of RBCs over a minimum of			
		16 wk with the same transfusion policy (defined below) compared with 16 wk			
		prior to treatment			
	On-treatment	Transfusion policy for the individual patient prior to therapy should be			
	RBC	maintained on treatment if not otherwise clinically indicated (documentation			
	transfusion	by the treating physician required); maximum variation between pre- and on-			
	policy	study practice of 1 g/dL (or 0.6 mmol/L) in terms of transfusion threshold			
-	se (pretreatment,	• Absolute increase of $30 \times 10^9/L$ for patients starting with $>20 \times 10^9/L$			
$<100 \times 109/L)$, HI-P	PLTs or			
		• Increase from $<20 \times 10^9/L$ to $>20 \times 10^9/L$ and by at least 100% In addition,			
		Evolution of bleeding symptoms is to be taken into account			
Neutrophil resp	nonse	At least 100% increase and an absolute increase >0.5 × 10 ⁹ /L			
	all patients), HI-N	(pretreatment, $<1.0 \times 10^9/L$)			
	relapse after HI				
l rogression or	reapse area in	For HI-N and HI-P:			
		At least 50% decrement from maximum response levels in			
		neutrophils or platelets, and not meet response criteria when			
		compared to baseline			
		For HI-E:			
		• Reduction in Hb by ≥ 1.5 g/dL, and not meet response criteria when			
		compared to baseline			
		Transfusion dependence			
		HTB: increase in transfusion burden by at least 50%			

Hb = hemoglobin; HI = hematologic improvement; PLTs = platelets; wk = week(s).

^{*}If patients received 1 or 2 RBC concentrates during the 16-wk pre-treatment period, it is recommended that HI-E achievement requires not only transfusion independence but also an increase of Hb by at least 1.5 g/dL (= 0.9 mmol/L).

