This study is a multicenter, open-label, Phase 2 study in adult patients with very low, low risk, or intermediate risk MDS per the International Prognostic Scoring System-Revised (IPSS-R) classification (see Appendix B).

The study will enroll up to 45 patients with MDS who will be evaluated for HI-E response composite derived from the MDS IWG 2018 criteria (modified by Platzbecker et al. 2019)

(see Appendix A). HI-E response assessment will be based on the individual patient's transfusion history in the 16 weeks prior to enrollment:

- NTD patients (received ≤ 2 RBC units for anemia within the prior 16 weeks): Hb increase of ≥ 1.5 g/dL over a continuous 8-week treatment period and no transfusion of RBC units for anemia over a continuous 8-week treatment period
 - Approximately 15 patients meeting the criteria for NTD may be enrolled in this study
- LTB patients (received 3 to 7 RBC units within the prior 16 weeks): No transfusion of RBC units for anemia over a continuous 8-week treatment period
 - Approximately 15 patients meeting the criteria for LTB may be enrolled in this study
- HTB patients (received ≥ 8 RBC units in the prior 16 weeks): ≥ 50% reduction in RBC units transfused over a continuous 8-week period.
 - Approximately 15 patients meeting the criteria for HTB may be enrolled in this study

Patients will be enrolled into a 48-week treatment period, including a 24-week Primary Treatment period and a 24-week Extension Treatment period. Patients demonstrating clinical benefit at the end of the 48-week treatment period may continue treatment. The dose of etavopivat is 400 mg once daily (QD) administered continuously; the selection of the starting dose is based on results from a Phase 1 study in patients with sickle cell disease (SCD) who were not receiving chronic RBC transfusions.

After the 6th patient completes a minimum of 4-weeks of daily etavopivat treatment, a safety review meeting will be held to confirm that the safety, exposure, and pharmacological response (PK/PD profile) are consistent with prior experience of etavopivat dosing in healthy volunteers and patients with sickle cell disease or thalassemia.

A futility assessment will be triggered when 15 patients across all strata or 8 patients in a single stratum reach 24 weeks of treatment, whichever occurs first. If both criteria are met at the same time, the overall futility assessment will be performed.

The futility criterion is defined as follows:

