5.1 Inclusion Criteria

Participants are eligible to be included in the study only if all the following criteria apply:

Informed Consent

1. Patient has provided documented informed consent; the informed consent form (ICF) must be reviewed and signed by each patient prior to any study-related assessments/procedures being conducted.

Age

2. Age \geq 18 years at time of first dose

Sex and Contraceptive/Barrier Requirements

3. Patients, if female and of childbearing potential, must agree to use acceptable methods of contraception and agree not to donate ova from study start to 90 days after the last dose of study drug, and who if male are willing to use acceptable methods of contraception and agree not to donate sperm, from study start to 90 days after the last dose of study drug.

Disease Specific Requirements

- 4. Documented diagnosis of idiopathic/de novo MDS according to 2016 WHO classification (see Appendix C) that meets IPSS-R classification (see Appendix B) of very low, low, or intermediate risk disease, and:
 - < 5% blasts and no Auer rods in bone marrow based on local pathology review
 - < Intermediate risk cytogenetic abnormalities per IPSS-R
- 5. Anemia defined as:
 - NTD: Subjects with mean Hb concentration < 10.0 g/dL on 2 measurements (1 performed within 3 days prior to W1D1 and the other performed 7 to 28 days prior to W1D1, not influenced by RBC transfusion within 7 days of measurement) and < 3 RBC transfusions for anemia in the prior 16 weeks before W1D1 of etavopivat dosing

OR

- Transfusion Dependent: Subjects having received ≥ 3 units of RBCs for the treatment of anemia within 16 weeks prior to W1D1
- 6. Serum erythropoietin level > 200 U/L, OR, if \leq 200 U/L, subject is non-responsive, refractory, or intolerant to erythropoiesis-stimulating agents, or erythropoiesis-stimulating agents are contraindicated or unavailable.
- 7. Eastern Cooperative Oncology Group performance status of ≤ 2 (see Appendix D)

- 8. Subject is non-responsive, refractory, or intolerant to luspatercept, or luspatercept is contraindicated or not indicated.
- 9. No alternative treatment options are available and/or appropriate for the subject, at the discretion of the investigator.
- 10. Patient is willing and able to adhere to the study visit schedule and other protocol requirements

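### The Appendix A progression row names no baseline for transfusion dependence or hemoglobin fall, so read literally it progresses stable LTB/HTB patients and some HTB responders at Week 16

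*Protocol*

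**What the plan says.** The progression row of Appendix A (the table adapted from the 2006 IWG criteria) gives blast thresholds and then three further lines, any one of which suffices. The granulocyte/platelet line is measured against the best response. The other two, "Reduction in Hb by ≥ 2 g/dL" and "transfusion dependence", have no reference. Stable disease in the same table is "Failure to achieve at least PR, but no evidence of progression for > 8 wks", so meeting any progression line rules it out.

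Inclusion criterion 5 (protocol 5.1) supplies the only working definition: "Transfusion Dependent: Subjects having received ≥ 3 units of RBCs for the treatment of anemia within 16 weeks prior to W1D1". LTB is 3 to 7 units in 16 weeks. The HTB stratum and its response are given as "HTB patients (received ≥ 8 RBC units in the prior 16 weeks): ≥ 50% reduction in RBC units transfused over a continuous 8-week period", so a responder may still be receiving transfusions.

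Baseline-relative wording does exist in the second Appendix A table, for example "HTB: increase in transfusion burden by at least 50" percent. That row covers only progression or relapse after hematologic improvement, and it also carries an unqualified transfusion-dependence line.

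Protocol 8.2.1 makes Appendix A the on-study disease assessment. Table 1-1 schedules it first at Week 16; Week 24 is hematologic improvement only. Section 7.2.1 lists disease progression among the reasons for which treatment must stop and points to no definition. The Efficacy Evaluable Set (protocol 9.2, SAP 2.1) requires the Week 24 Response visit, and SAP 3.8 allows discontinued patients to be replaced.

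**The concern.** A criterion that two of the three strata satisfy before the first dose cannot separate worsening from no change. As written, it leaves a transfused patient with an unchanged burden without a stable-disease category, and it conflicts with the protocol's own HTB response. The hemoglobin line has the same gap with a milder consequence. A reduction implies some comparator, so stable patients are not caught automatically, but a fall measured from a transfusion-raised value could be.

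The label matters because it is attached to a compulsory stop. A patient taken off treatment at Week 16 has no scheduled Week 24 visit, so leaves the primary denominator and may be replaced. Losing non-responders this way raises the observed response rate; losing HTB responders lowers it.

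**Working it through.** **The plan's own figures.** Exact binomial, n = 45, null rate 20%, alternative 40%, one-sided 0.025 (protocol 9.3). The smallest critical value is 15 responders: P(X ≥ 15 | 0.20) = 0.0250 and P(X ≥ 15 | 0.40) = 0.857, against a stated power of 87.3%. The futility probabilities reproduce: P(X ≤ 3 | 15, 0.40) = 0.0905 and 0.75^8 = 0.1001.

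**Who meets the line at entry.** 15 LTB + 15 HTB = 30 of 45 planned patients.

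**Stable patients at W16D1.** The target is Day 106 (SAP Table 3), so 105 days on treatment. An unchanged burden of b units in 112 days gives b × 105/112: 2.81 for b = 3, 3.75 for b = 4, 6.56 for b = 7, 7.5 for b = 8. Only the lowest LTB burden is borderline; the rest stay at or above 3.

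**HTB responders.** A 50% cut leaves 4 units from 8, 5 from 10 and 6 from 12, all at or above 3. To get down to 2 units the reduction must be 6/8 = 75%, 8/10 = 80% or 10/12 = 83%, whereas HI-E asks for 50%. An 8-week response can be complete by Day 106, so both labels can apply at the same visit.

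**Illustration on the planned test (protocol 9.6.1).** The removal rates here are assumptions; no document supplies them. Removed patients are replaced, so n stays at 45.

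- Transfused non-responders (two thirds of non-responders) removed at rate q, true rate 20%: p = 0.2 / [0.2 + 0.8(1 − 2q/3)].
- HTB responders (one third of responders) removed at rate s, true rate 40%: p = 0.4(1 − s/3) / (1 − 0.4s/3).

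| Assumed removal | p | Result |
|---|---|---|
| q = 2% | 0.2022 | error 0.0273 |
| q = 5% | 0.2055 | error 0.0313 |
| q = 10% | 0.2113 | error 0.0391 |
| s = 10% | 0.3919 | power 0.831 |
| s = 25% | 0.3793 | power 0.783 |
| q = s = 10%, true 20% | 0.2057 | error 0.0315 |

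**Candidate replacement rule for LTB/HTB**, judged once at Day 106: units at least 50% and at least 3 above the 16 weeks before W1D1. It was simulated with gamma-distributed transfusion intervals; the coefficient of variation (CV) is an assumption, 0.15 to 0.30, with 1.0 for fully random timing.

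| Scenario | Literal line | Baseline-relative rule |
|---|---|---|
| Stable, LTB | 74–100% labelled | 0–4.9% (a repeat run gave a maximum of 5.1%) |
| Stable, HTB | 100% | 0–4.1% |
| HTB burden halved | 73–100% | 0.0% |
| Burden doubled, LTB / HTB | – | 53–100% / 82–100% detected |
| Stable, fully random timing, LTB / HTB | 56–85% / 89–99.5% | 6–24% / 3–17% |

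The single look matters. If the same rule is applied over any rolling 16 weeks, at CV 0.30 it labels stable patients in up to about 19% (LTB) and 18% (HTB) by Week 24, and 33% of each by Week 48. A rolling 3-unit rule for NTD, with no allowance for the patient's own history, labels a stable patient on 1 unit per 56 days in about 52% by Week 24.

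**The case against.** The literal reading defeats itself: it would progress two thirds of the planned patients before dosing, in a protocol that recruits them, writes transfusion plans for them and, in the SAP, tabulates their burden to Week 48. The row's title implies worsening, and applying an entry category on treatment is an inference. This stands as an account of how most investigators would act, and it keeps the point to a drafting gap. It does not supply the missing threshold: even on the sensible reading, sites have no stated rule for how much more transfusion is progression before a response has occurred.

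A reader might infer three stronger conflicts that the documents do not support.

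- The 16-week HTB category, "Minor response: Reduction by at least 50% of RBCs over a minimum of" 16 weeks, cannot yet be complete at W16D1. Day 106, with a protocol window to Day 109, falls short of 112 days. Only the 8-week HI-E conflict survives.
- An LTB patient transfused early and then free of transfusion for 8 weeks is not a clear contradiction, because Appendix A itself uses 8 weeks without transfusion as transfusion independence.
- The error figures do not show that the trial's test was inflated. They rest on assumed removal rates, and losses can run in either direction.

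It is also fair to say that a stable non-responder can leave through the lack-of-efficacy or investigator-decision reasons in 7.2.1, whatever Appendix A says. That stands, and the denominator fix has to cover those routes too.

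**Conclusion.** The gap is real and should be closed. As written, about 30 of 45 planned patients meet a progression criterion at entry, and an HTB patient can meet HI-E and progression at the same Week 16 visit. This rests on carrying the 3-units-in-16-weeks entry definition onto treatment, the only definition available.

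The documents do not show that any patient was stopped for this reason. The frequency of literal use is unknown and the net direction of bias is not fixed. The study ended early (SAP 1.1), overall response rate and duration of response are dropped (SAP 5.2), and MDS response goes to listings (SAP 4.2.1.1). In the abbreviated report the effect is therefore confined to who remains in the Efficacy Evaluable Set. Confidence is medium: the text is certain, the practical consequence is not.

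**What to change.** 1. **Transfusion line.** Replace it with a rule judged only at scheduled MDS response assessments, never over any rolling window. LTB/HTB: RBC units in the preceding 16 weeks (15 weeks at W16D1) at least 50% and at least 3 units above the 16 weeks before W1D1. NTD: at least 3 units in that period, and at least 3 above the patient's own 16-week pre-treatment count. The 3-unit floor never binds in HTB, where 50% of 8 is already 4. In LTB it keeps a move from 4 to 6 units from counting. The NTD version has not been simulated.
2. **Hemoglobin line.** State that the fall is from baseline and is confirmed on a second value, with neither value within 7 days after an RBC transfusion. The NTD entry measurements already use such a window ("not influenced by RBC transfusion within 7 days of measurement"). Suitable baselines already exist: the mean pre-transfusion value in protocol 8.2.2.1 for LTB/HTB and the SAP 3.3 mean for NTD.
3. **Section 7.2.1.** Cite this row at the disease-progression reason.
4. **Denominator.** In the Efficacy Evaluable Set definition (protocol 9.2, SAP 2.1) and SAP 4.2.1, with SAP 3.8 aligned, keep every treated patient who stops before Week 24 for progression, lack of efficacy or investigator decision. Count the patient as a non-responder unless HI-E was already met. SAP 3.11 already counts discontinuations before HI-E assessment as non-responders in its informal futility look.

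The cost is two lines in Appendix A, one cross-reference and coordinated edits to the analysis-set, counting and replacement text. In use, expect an occasional repeat hemoglobin and a slightly lower observed response rate.
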